#### **Specific aim:**

- To study the oxidative and inflammatory effects of exposure to diesel exhaust on the respiratory epithelium and the olfactory nerve in healthy individuals. Additionally, the study aims to determine whether these exposures result in measurable effects on the sense of smell and cognitive ability.

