## **Project Description**

The studies will be conducted using our well-established techniques and methods. Exposure to controlled levels of motor exhaust from diesel fuel has been conducted for more than two decades, and in recent years we have also developed a collaboration with Associate [name] group at the Thermochemical Energy Conversion Laboratory (TEC-Lab) at Umeå University. This offers a unique opportunity to study under different combustion conditions.

**Hypothesis:** Diesel exhaust cause cell dysfunction in the olfactory system secondary to mitochondrial dysfunction and oxidative stress. Additionally, we hypothesize that these exposures result in measurable effects on the sense of smell and cognitive ability.

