**Hypothesis:**

Diesel exhaust gases cause cell dysfunction in the olfactory system secondary to mitochondrial dysfunction and oxidative stress. The hypothesis also includes studying whether exposures lead to measurable effects on the sense of smell and cognitive abilities.

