### Olfactory Testing

The Sniffin' Sticks test (Hummel et al., 1997), a commercially available test, will be used to determine the participant's odor detection threshold. The odorant (n-butanol) is presented in marker pens filled either with n-butanol or a blank (no odor). The test uses 16 concentrations of n-butanol, from the weakest concentration (1.2 ppm n-butanol) to the strongest (4% n-butanol). In a "triple-forced-choice paradigm," the detection threshold is determined using a staircase method (Doty, 1991). Three pens are presented in a randomized order—two with blank stimuli and one with the odorant at a given concentration. The participant's task is to identify which pen contains the odorant.

Participants wear eye masks to prevent visual identification of the pens. The pen is placed approximately 2 cm below the nostrils for about 3 seconds. The test starts at the 8th concentration level, and if the participant correctly identifies the odorant four times in a row,

the test continues with higher concentrations. If the participant fails to do so, the test proceeds to lower concentrations.

The test has good test-retest reliability (Albrecht et al., 2008) and validity (Ribeiro et al., 2016). The exposure levels of n-butanol are much lower than the occupational exposure limit of 15 ppm (45 mg/m^3), so no toxic effects or discomfort risks are expected.

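### The odour-threshold staircase is written with both step directions reversed, so it cannot find the threshold it is meant to measure

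*Protocol*

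**What the plan says.** The Olfactory Testing section names a commercial pen test that "will be used to determine the participant's odor detection threshold" and states that "the detection threshold is determined using a staircase method". The scale has 16 n-butanol concentrations, listed from the weakest (1.2 ppm) to the strongest (4%). Each presentation uses three pens, "two with blank stimuli and one with the odorant at a given concentration".

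The stepping rule follows: "The test starts at the 8th concentration level, and if the participant correctly identifies the odorant four times in a row", then "the test continues with higher concentrations. If the participant fails to do so, the test proceeds to lower concentrations". No other section gives a different direction.

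Smell is a stated target of the study. The Specific aim asks "whether these exposures result in measurable effects on the sense of smell and cognitive ability". The first statement of the hypothesis, under Project Description, says "we hypothesize that these exposures result in measurable effects on the sense of smell and cognitive ability", and the separate Hypothesis section repeats the point as "studying whether exposures lead to measurable effects on the sense of smell and cognitive abilities".

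**The concern.** A detection threshold is the weakest concentration that a participant reliably detects. To find it, a staircase has to make the task harder after a success and easier after a failure, so that the presented level swings back and forth around the threshold. The protocol does the opposite in both branches. A participant who detects level 8 is moved to stronger, easier pens. One who does not is moved to weaker, harder pens.

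The stated procedure therefore contradicts its stated purpose. If it were followed, most of the information on the smell outcome would be lost, and a modest shift between diesel exhaust and filtered air would mostly go unseen. The biopsy, blood and cognitive outcomes are not affected.

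**Working it through.** The protocol gives no figure to reproduce here. The contradiction follows from logic, provided that detection improves with concentration. The calculations show how much a literal reading would cost.

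**From the protocol**
- 16 levels, start at the 8th.
- Three pens, one with odorant, so the chance of a correct guess is 1/3.
- Passing a level means four correct in a row. By guessing alone that has probability (1/3)^4 = 1.2%.

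**Assumed, not in the protocol**
- Logistic detection curve with slope 1.0, 1.5, 2.0 or 3.0 per level.
- True threshold T equally likely at levels 3 to 13.
- Steps of 1 or 2 levels.
- Start at level 8 or 9 counted from the weakest pen, because the numbering is not stated.
- As-written runs stop at an end of the scale or after 7 reversals. Swapped runs stop after 7 reversals or on leaving the scale.

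**Formulas**
- P(correct at level L) = 1/3 + 2/3 × logistic(slope × (L − T)).
- P(pass level L) = P(correct)^4.

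**Step 1: the balance point.** Passing and failing are equally likely when P(correct) = 0.5^(1/4) = 0.841. Then logistic = (0.841 − 0.333) × 1.5 = 0.761, and its logit is 1.16. At slope 1 the balance point is therefore 1.16 levels above T. Above it, passing is more likely than not; below it, failing is. With success leading to weaker pens, both sides are pushed back towards this point. With success leading to stronger pens, as written, both sides are pushed away.

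**Step 2: exact check of where as-written runs end** (slope 1.5, start at level 8, 1-level steps, treated as a random walk with the pass probabilities above).

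| True threshold | P(pass level 8) | P(run ends at strongest pen) |
|---|---|---|
| 5 | 0.971 | 0.999 |
| 7 | 0.595 | 0.62 |
| 8 | 0.198 | 0.13 |
| 9 | 0.043 | 0.006 |

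For T = 8, for example, P(correct) at level 8 is 1/3 + 1/3 = 2/3, and (2/3)^4 = 0.198. The end point is almost settled by whether level 8 is detectable. Thresholds of 9 and above all look alike, and so do those of 5 and below.

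**Step 3: simulation** (4,000 runs for each of the 11 thresholds, at every combination of slope, start, step size and direction).

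| | As written | Directions swapped |
|---|---|---|
| Information on T, 1-level steps | 0.84–0.89 bits | 2.33–3.27 bits |
| Information on T, 2-level steps | 0.70–0.87 bits | 2.09–2.77 bits |
| Best estimate within 1 level of T | 36–40% | 88–100% |
| Median number of levels presented | 4–8 | 10–14 |

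Information is log2(11) = 3.46 bits minus the mean posterior entropy given every pass/fail result, so it assumes no scoring rule. The best estimate is the posterior mean. With no test at all, always guessing level 8 is within 1 level for 3 of 11 thresholds, or 27%.

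As written, 99.9–100% of runs reach an end of the scale, with a median of 0 reversals. No reversal occurs in 85–95% of runs with 1-level steps and in 93–98% with 2-level steps.

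**Step 4: separate check with a different stopping rule** (slope 1, start at level 8, 60 one-level steps, 3,000 runs per case). As written, every run spent its last 20 steps on levels 1–2 or 15–16. The share finishing at the strong end was 100%, 97.9%, 9.4%, 0% and 0% for T = 3, 5, 8, 11 and 13. With the directions swapped, the mean level over the last 20 steps was 4.2, 6.2, 9.2, 12.2 and 14.2. That is about 1.2 levels above T throughout, as Step 1 predicts.

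**The case against.** The strongest reply is that the named commercial test governs and the two sentences are a short paraphrase with a slip in it. The protocol gives no step size, reversal count, stopping rule or score, so nobody could run the test from this text alone, and staff would turn to the kit's instructions. This stands as a limit on the likely harm. It does not make the stated rule right: anyone running, auditing or repeating the test from the protocol has the wrong rule.

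A second reply is that pen numbering may be behind the wording. The protocol does not say whether level 1 is the weakest or the strongest pen, and a higher level may have been confused with a higher concentration. That is a plausible origin for the error but not a reading that rescues the text, because the direction is given in concentrations.

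Third, the simulated sizes rest on assumptions. The 27% comparator depends on thresholds spread evenly over levels 3–13; spread evenly over 6–10, guessing level 8 would be within one level for 3 of 5, or 60%. Swapped runs are also longer, so part of the information gap comes from run length. Both points are fair. They affect the sizes, not the contradiction.

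Finally, smell comes second in the specific aim, after the oxidative and inflammatory effects. That is true, but it remains a stated aim and part of the hypothesis.

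**Conclusion.** The concern holds. The section sets out to determine a detection threshold by a staircase and then gives step directions that move away from it, in both branches. That conclusion needs only that detection improves with concentration.

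Followed literally, a run yields roughly a pass or fail at about level 8: at most 0.89 of 3.46 bits, against at least 2.09 bits with the directions swapped. Those sizes describe single simulated runs under the assumed curves, threshold spread, step sizes and stopping rules. Any bias in the comparison of diesel exhaust with filtered air would depend on a scoring rule that the protocol does not state, so no direction or trial-level size is claimed. Because staff may be following the commercial test's own instructions, this is a point that should be fixed rather than evidence that the outcome has been lost.

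**What to change.** Swap the two directions in the Olfactory Testing section. After four correct identifications in a row the test should move to weaker concentrations; otherwise it should move to stronger ones.

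Then confirm that the procedure actually used at the site runs this way, and check the four-in-a-row criterion against the commercial test's instructions at the same time. Step size, reversals, stopping and scoring can be left to that test's procedure.

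The cost is two words exchanged and one confirmation. No participants, visits or tests are added.

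### Do the pen strengths in the smell test contradict the statement that n-butanol exposure is far below the 15 ppm limit?

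*Protocol*

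**What the plan says.** The Olfactory Testing section of the protocol describes an odour detection threshold test with n-butanol, "presented in marker pens filled either with n-butanol or a blank (no odor"). "The test uses 16 concentrations of n-butanol", running "from the weakest concentration (1.2 ppm n-butanol) to the strongest (4% n-butanol"). Each pen is held about 2 cm below the nostrils for about 3 seconds. "The test starts at the 8th concentration level", and the text does not say from which end of the series the levels are counted.

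The section closes with a safety statement: "The exposure levels of n-butanol are much lower than the occupational exposure limit of 15 ppm" (also given as 45 mg/m3), "so no toxic effects or discomfort risks are expected". It gives no n-butanol concentration in the air at the nose, no number of presentations per session and no averaging time for the limit.

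**The concern.** The only n-butanol concentrations in the protocol are the pen strengths, and most of them are far above 15 when put on the same ppm scale. Only the weakest pens look much lower than 15. A reader may therefore suspect that the authors set the weak end of the pen series against the limit and overlooked the strong end, or confused a liquid dilution with an air concentration.

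The comparison is also the only reason the section gives for expecting no toxic effects or discomfort. If it were wrong, the stated safety basis of the smell test would fall away and the risk description would need correcting.

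**Working it through.** **Inputs from the protocol (Olfactory Testing):** 16 strengths; weakest 1.2 ppm; strongest 4%; start at the 8th level; about 3 seconds per pen; limit 15 ppm, or 45 mg/m3.

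**Assumptions, not in the protocol:** a constant ratio between neighbouring strengths; molar mass of n-butanol 74.12 g/mol; molar volume of air 24.06 to 24.45 L/mol (20 to 25 °C).

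**1. The pen series.** 4% = 40,000 ppm. Sixteen strengths are separated by 15 steps, so the implied ratio is (40,000 / 1.2)^(1/15) = 2.002. Conversely, 40,000 / 2^15 = 1.22 ppm, against the stated 1.2. Both end points therefore fit one two-fold dilution series on one scale, that of the pen content.

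**2. The limit.** mg/m3 = ppm × molar mass / molar volume. This gives 15 × 74.12 / 24.45 = 45.5 and 15 × 74.12 / 24.06 = 46.2 mg/m3, against the stated 45. The two forms of the limit agree as a concentration of vapour in air. The one conversion the protocol makes is sound.

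**3. The numerical comparison that raises the alarm.**

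| Level from the weak end | Pen content (ppm) | Numerically above 15? |
|---|---|---|
| 1 to 4 | 1.2, 2.4, 4.8, 9.6 | no |
| 5 to 8 | 19.3, 38.6, 77, 155 | yes |
| 9 to 12 | 310, 621, 1,243, 2,489 | yes |
| 13 to 16 | 4,983, 9,977, 19,977, 40,000 | yes |

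Twelve of 16 are above 15. With equal arithmetic spacing instead, 15 of 16 would be. The starting level is about 155 ppm counted from the weak end and about 310 ppm counted from the strong end.

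**4. What the comparison can show.** Steps 1 and 2 establish that the two ppm figures measure different things: pen content and vapour in air. The quotients are 40,000 / 15 = 2,667 for the strongest pen, and 155 / 15 = 10.3 or 310 / 15 = 20.7 for the starting pen. They are not multiples of the limit. They are the reductions from pen content to inhaled air that would bring the air figure down to 15 ppm. The protocol does not give the actual reduction, so it cannot be checked against these values.

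**5. Averaging time.** The protocol does not give the period over which the limit applies. To illustrate only, suppose there were no reduction at all between pen and air, and take one 3-second presentation of the strongest pen. Averaged over an assumed 15 minutes, this is 40,000 × 3 / 900 = 133. Averaged over an assumed 8 hours, it is 40,000 × 3 / 28,800 = 4.2. The first is above 15 and the second below it. The answer turns on quantities that the document does not contain.

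**The case for a change.** The strongest case for a correction is that the protocol draws its no-risk conclusion directly from this comparison, and the comparison cannot be derived from the figures printed beside it. Two unlike quantities both appear as ppm, without a label. The strongest pen needs no assumption about spacing to stand at 40,000 ppm. Nor can a reader assume that only weak pens are used, because the staircase as written moves to higher concentrations after four correct answers in a row. The remedy would cost one short calculation and one sentence.

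Most of this is true, but it proves less than it seems to. It shows that the statement is unsupported on the page, which is weaker than showing it wrong. The protocol's sentence is about exposure levels, not pen contents, and it does not tie the 15 ppm to any particular pen. A mix-up of units is one reading; the other is that the authors meant inhaled air, given the short presentation at a distance. The direction of the staircase is a separate question, and it does not supply the missing air concentration.

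What stands is that the basis of the comparison is not written down and that the unlabelled units invite misreading.

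**Conclusion.** The concern does not call for a change. The pen arithmetic is right: the strongest pen is 40,000 ppm, and 12 of 16 strengths are numerically above 15 under the two-fold spacing that the end points imply. But it sets liquid strength against an air limit, so it does not show that the exposure statement is false. Whether the statement is true depends on the reduction from pen to air and on the averaging time, and the document gives neither.

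What remains is a missing supporting calculation for a safety sentence about a commercially available test. The sentence has no role in the allocation, the threshold measurement, the sample size, the power or the error rates. Supplying the calculation, or softening the wording, would leave the conduct of the test and every result and conclusion as they are, provided that the air figure is acceptable. Labelling 1.2 ppm and 4% as concentrations of the pen content would help a reader, but this is optional.

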### Cognitive Testing

Cognitive ability will be assessed using the Letter Digit Substitution Test, a paper-and-pencil test that evaluates working memory, processing speed, and attention. A key at the top of the page provides the correct mapping for the numbers 1 to 9, which are paired with specific letters. Below the key, there are 120 letters (9 different ones), each connected to a blank square. The participant's task is to write as many numbers as possible in the empty squares under a 60-second time limit according to the letter-number mapping provided in the key.

The test has good test-retest reliability (Hoex et al., 2002) and validity (Natu & Agarwal, 1995). There is no risk of pain or discomfort associated with the test.

### Blood Tests

Blood samples will be taken before exposure and before olfactory epithelium biopsies. These will be analyzed for cell count, inflammation markers, and lymphocyte subtyping using flow cytometry. A maximum of 100 ml of blood will be drawn during each exposure.

The effects of exposure to air pollution at the cellular level will be studied in monocytes from peripheral blood using in-vitro tests. Further analyses, including PCR (polymerase chain reaction), will be conducted for the APOE gene, a genetic factor that can influence sensitivity to air pollution. These analyses will be performed at Kuopio University, Finland.

RNA sequencing and DNA methylation will also be conducted to identify biomarkers for acute exposure to air pollution at the Institute of Experimental Medicine, Czech Academy of Science, Czech Republic.

### COVID-19 Testing

Participants will be tested for SARS-CoV-2 before each exposure session.

### Significance

Air pollution causes significant health effects on the lungs, cardiovascular system, and nervous system, which affects many patients and places a heavy burden on healthcare systems, with societal costs exceeding 40 billion SEK annually in Sweden. Our research aims to deepen the understanding of the multifaceted health effects of air pollution, which impacts various organ systems. This is especially important as we have previously shown that current medications do not prevent the full extent of the health effects of air pollution. Advanced research will lead to a better understanding and the potential development of more effective interventions, which is crucial for health as well as for industries and authorities.

we are one of the few research groups with the knowledge and resources to conduct human exposure studies to examine this specific type of combustion and subsequently investigate its health effects using unique and advanced methods. Therefore, this project is highly significant in increasing our knowledge of how diesel exhaust negatively affects the olfactory nerve, which is crucial for understanding the mechanisms behind the health effects of air pollution, such as the development of cognitive decline and dementia. The findings may have important implications for public health policies and strategies to mitigate the impact of air pollution on cognitive health.
